#### ***9.5.2.9 Erectile Function***

The IIEF is a commonly used, validated instrument that consists of 15 items. Five subscales are calculated as follows:

- Erectile Function (items 1, 2, 3, 4, 5, 15)
- Orgasmic Function (items 9, 10)

- Sexual Desire (items 11, 12)
- Intercourse Satisfaction (items 6, 7, 8)
- Overall Satisfaction (items 13, 14)

Each subscale will be summarized separately for both treatment groups for the baseline (defined as pre-PAE for the PAE group and pre-RALRP for the Control group), 3 month, 6 month, 9 month, and 12 month timepoints, including change from baseline. Treatment means for the change from baseline will be compared using a matched pairs t-test.

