### **2.2 Secondary Objectives**

The key secondary objectives are to assess the outcomes listed below and to compare the results for patients who receive PAE and those that do not:

1. Change in hemoglobin on RALRP post operative day (POD) 1 compared to baseline
2. Change in hematocrit on RALRP post operative day (POD) 1 compared to baseline
3. Change in prostate volume between baseline and Visit 3 (6 weeks  $\pm$  2 weeks post PAE) as determined by MRI in patients who receive PAE
4. Blood transfusion requirements during RALRP
5. RALRP duration in minutes
6. Length of hospital stay for RALRP
7. Presence or absence of a complete surgical margin around the entire tumor as determined by histopathology examination post RALRP
8. Biochemical recurrence of prostate cancer as determined by PSA levels post RALRP at 1 year follow up
9. Return to continence post RALRP as assessed by the pad weight test.
10. RALRP related adverse events
11. Erectile function compared to baseline as assessed by the IIEF post RALRP at 1 year follow up.

Additional secondary objectives are to assess outcomes listed below for patients that receive PAE:

12. Change in PSA between baseline and Visit 3 (6 weeks  $\pm$  2 weeks post PAE)
13. PAE related adverse events
14. Histologic changes in the prostate after PAE

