### **3 PAE Patient Population**

#### **3.1 Inclusion Criteria**

Patients must meet all of the following inclusion criteria in order to be entered into the study:

1. Patient is 45-79 years old
2. Patient has signed informed consent
3. Patient must have biopsy-proven prostate adenocarcinoma with localized disease
4. Patient must be a candidate for robot-assisted radical prostatectomy (RALRP)
5. Patient has a prostate size >40 grams

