## 4 Study Design

This is a phase 2, prospective, non-randomized, matched-pair, single center study designed to evaluate the safety and efficacy of PAE using Embosphere Microspheres as a pre-operative tool in patients with biopsy-proven adenocarcinoma of the prostate with localized disease. A total of 10 patients with biopsy-proven prostate carcinoma with localized disease will be enrolled in the study to receive pre-prostatectomy PAE, and matched with 10 controls who will not receive pre-prostatectomy PAE, in order to evaluate the study objectives. Patient recruitment is anticipated to take approximately 2 years. Duration of participation is expected to be approximately 15 months from time of enrollment, including a minimum of 12 months follow up. This study will have a stop limit for re-evaluation after two patients with serious adverse events attributed to confirmed or suspected non-target embolization have been identified.

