### 4.2 Control Patients

A similar cohort of patients who undergo RALRP without PAE will be treated as a matched control group. The controls will be matched using a 1:1 ratio to PAE treated patients based on AUA risk group. Risk stratification will be as follows, according to AUA guidelines:

- Low risk: Stage T1c to T2a tumors, AND PSA  $\leq 10$ ng/mL, AND Gleason score  $\leq 6$

- Intermediate risk: Stage T2b tumors, OR PSA > 10ng/mL but ≤ 20ng/mL, OR Gleason score 7
- High risk: Stage T2c or higher tumors, OR PSA > 20ng/mL, OR Gleason score 8-10

Control patients will be selected after 10 patients for the PAE arm have been identified, such that the first potential control patient who matches the risk score of a PAE patient and agrees to participate in the study is matched to the appropriate member of the PAE arm. Once a match is identified, additional matches for a single PAE patient will not be sought. Because we are matching PAE and control patients based on AUA risk score only, we do not anticipate difficulty in finding a matched control for every PAE patient.

Control patients will sign written informed consent before any study-specific assessments are performed. Patients will complete EPIC and IIEF questionnaires within 12 weeks prior to RALRP, and will undergo MRI as a baseline study. Oncologic and functional outcomes will be evaluated by assessing PSA, EPIC, and IIEF at months 3, 6, 9, and 12 post RALRP, and then annually per standard follow-up protocol for the treating institution.

Safety will be evaluated for PAE patients throughout the study treatment and assessment periods by assessing adverse events, concomitant medications, changes in laboratory values, and findings on physical examination. Safety will be evaluated for Control patients during RALRP and the follow up period by assessing adverse events and concomitant medications.

The patients in both groups will continue to be followed post RALRP according to standard follow up protocol for the treating institution.

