### **9.2 Sample Size Calculations**

This is a proof of concept study and therefore, formal sample size calculations were not performed. Ten patients will be assigned in a non-randomized sequential manner to the PAE treatment group. Ten patients will also be assigned as matched controls in a 1:1 ratio to PAE treated patients based on risk group as defined in section 4.2. This sample size will provide sufficient data to assess the preliminary safety and efficacy of PAE treatment prior to RALRP.

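### IIEF change scores are compared without baseline adjustment between non-randomized arms matched on AUA risk group only, so a systematic baseline difference would pass in part into the estimated PAE effect

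*Combined protocol and SAP*

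**What the plan says.** Section 2.2 lists among the key secondary objectives: "Erectile function compared to baseline as assessed by the IIEF post RALRP at 1 year follow up". Section 9.5.2.9 summarizes five IIEF subscales by arm at baseline and at 3, 6, 9 and 12 months. Baseline is "defined as pre-PAE for the PAE group and pre-RALRP for the Control group". The between-arm test is then specified: "Treatment means for the change from baseline will be compared using a matched pairs t-test". No covariate is named there, and the general considerations in Section 9.1 add neither a baseline-adjusted model nor a sensitivity analysis.

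On design, Section 4 states: "This is a phase 2, prospective, non-randomized, matched-pair, single center study". Section 4.2 describes the pairing: "The controls will be matched using a 1:1 ratio to PAE treated patients based on AUA risk group". Risk group is built from stage, PSA and Gleason score. Section 4.2 confirms that nothing else enters the match: "Because we are matching PAE and control patients based on AUA risk score only". There are 10 patients per arm, and Section 9.2 says of the size: "This is a proof of concept study and therefore, formal sample size calculations were not performed".

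**The concern.** Risk group contains no measure of erectile function, age or prostate size, so the pairing does nothing to balance baseline IIEF. A systematic difference is also possible. The criterion "Patient has a prostate size >40 grams" and the age range stand under the PAE patient population. Section 4.2 calls the controls similar, but it states no such limits for them and takes the first risk-matched man who agrees.

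Comparing raw change treats a point lost from any starting level as the same. The scoring in Appendix E bounds the Erectile Function subscale at 1 to 30 (items 1 to 5 score 0 to 5, item 15 scores 1 to 5). A man who starts at 2 can lose 1 point at most; a man who starts at 28 can lose 27. If surgery pulls scores towards the floor, the arm that started worse will show the smaller loss, and this would be read as an effect of PAE, or of its absence, on erectile function.

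**Working it through.** **The plan's own figure.** There is none to reproduce: the documents give no SD, slope, correlation or target difference for the IIEF.

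**Bias.** Assume no PAE effect and follow-up = a + b x baseline + error. The mean change in an arm is then a - (1-b) x (its baseline mean). With D the amount by which one arm's baseline mean is lower, the expected difference in change is (1-b) x D in favour of that arm. For D = 5:

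- b = 0.2: 0.8 x 5 = 4.0 points
- b = 0.3: 0.7 x 5 = 3.5
- b = 0.4: 0.6 x 5 = 3.0
- b = 0.5: 0.5 x 5 = 2.5
- b = 0.7: 0.3 x 5 = 1.5

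The bias is zero if b = 1 or D = 0.

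**Error rate and precision.** I simulated 40,000 trials per scenario with 10 pairs. The planned matched pairs t-test on change (9 df) was compared with an ANCOVA of the follow-up score on arm, risk group and baseline score (20 patients, 20 - 5 = 15 df). Assumptions not in the documents: the SDs below, normal scores, two-sided 5% level, risk groups split 4/4/2 among the pairs, no IIEF correlation within pairs, complete follow-up.

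| b | Baseline SD | Residual SD | Planned test, false positives at D=0 | Same at D=5 | Planned CI half-width, D=0 | ANCOVA CI half-width, D=0 | ANCOVA narrower by |
|---|---|---|---|---|---|---|---|
| 0.2 | 10 | 6 | 5% | 12% | 9.83 | 5.81 | 41% |
| 0.3 | 8 | 7 | 5% | 12% | 8.84 | 6.79 | 23% |
| 0.4 | 9 | 7 | 5% | 10% | 8.69 | 6.78 | 22% |
| 0.5 | 8 | 7 | 5% | 9% | 7.95 | 6.79 | 15% |
| 0.7 | 8 | 5.7 | 5% | 8% | 6.10 | 5.53 | 9% |

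Under this model the ANCOVA estimate was within 0.1 point of zero and its false-positive rate was about 5% in every row, at D = 0 and at D = 5. With D = 5 its interval was 9 to 39% narrower for b = 0.2 to 0.5 and 4% narrower at b = 0.7.

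Part of the gain is degrees of freedom: the t multiplier falls from 2.262 (9 df) to 2.131 (15 df), and 1 - 2.131/2.262 = 6%. At b = 0.7 that is most of the gain.

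**Chance imbalance.** With SD 8 and 10 per arm, the baseline mean difference has SE 8 x sqrt(2/10) = 3.6, so a difference of 4 points or more arises by chance 26% of the time. This variation is already in the standard error of the change score, which is why the D = 0 column stays at 5%.

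**When ANCOVA is the biased one.** If the arms differ in stable true function and would change in parallel, the change score is unbiased. ANCOVA is then off by (1 - reliability) x D in favour of the arm that started better. For D = 4 that is 2.0, 1.2 and 0.4 points at reliability 0.5, 0.7 and 0.9.

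**The case against.** The strongest reply is that, without randomization, baseline adjustment is not automatically right. The last calculation shows that the change score is correct under parallel change, and the objective itself asks about function relative to baseline. This stands, and it is why the change-score test should be kept. The bounded scale makes parallel loss after prostatectomy doubtful, but the documents cannot settle it. A straight-line adjustment is also only an approximation near the floor.

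It also stands that D and b are unknown, that no document reports an actual IIEF difference between the arms, and that at b = 0.7 both bias and precision gain are small. Baseline scores are tabulated by arm, so an imbalance would be visible, though not corrected. This is one secondary endpoint in a 10-pair proof-of-concept study.

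A reader might infer more than the documents support:

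- *Chance imbalance invalidates the test.* It does not; the error rate stays at 5%.
- *The comparison could come out with the wrong sign.* The calculation assumes no PAE effect, so there is no sign to reverse.
- *Regressing within-pair differences on within-pair baseline differences is the same fix.* It is a different model with 8 df. In the same simulations at b = 0.7 it gained nothing at D = 0 and gave an interval about 10% wider than the planned one at D = 5.
- *The same adjustment carries over to hemoglobin and hematocrit.* Sections 9.5.2.1 and 9.5.2.2 take baseline on the day of surgery, which in the PAE arm comes after PAE. That covariate could itself be affected by treatment. The IIEF baseline is taken before PAE and does not have this problem.

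**Conclusion.** The concern holds in a limited form. The planned comparison leaves baseline IIEF unadjusted in arms that neither randomization nor matching balances on it. A systematic 5-point baseline difference would shift the estimate by 2.5 to 4.0 points at slopes of 0.2 to 0.5 and by 1.5 points at 0.7, always towards the arm that started worse, and would raise the false-positive rate from 5% to between about 8 and 12%. These shifts are well inside the planned test's own CI half-width of roughly 6 to 10 points, so the distortion is moderate. They rest on an assumed slope, assumed SDs and an assumed systematic difference. Chance imbalance brings a loss of precision, not an inflated error rate. Baseline adjustment does not remove other differences between the arms. The change is worth making because it needs no new data; the estimated blood loss result is not touched.

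**What to change.** In Section 9.5.2.9, for each subscale and follow-up visit, make the between-arm comparison an ANCOVA of the follow-up score on arm, AUA risk group and baseline score, reported with a 95% CI. Name month-12 Erectile Function as the main one of these, in line with the objective. Use the baseline already defined there (before PAE or before RALRP), not the Visit 3 score. Risk group is the only matching factor, so including it as a covariate carries the matching into the model.

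Keep the matched pairs t-test on change as a prespecified sensitivity analysis, and state why: the two analyses rest on different assumptions and, in the two cases worked through above, err in opposite directions when the arms differ at baseline. Agreement between them would be reassuring; disagreement should be reported as uncertainty about the effect.

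The cost is SAP wording and one degree of freedom for the baseline covariate. Both arms already complete the IIEF at Visit -1.

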## **9.5 Efficacy Analyses**

### **9.5.1 Primary Efficacy Outcome – Estimated Blood Loss**

The primary efficacy outcome is the estimated blood loss (EBL) during RALRP. The amount of EBL will be recorded in ccs, and the data will be summarized separately for both treatment groups, including 95% confidence intervals for the means. Treatment means will be compared using a matched pairs t-test.

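### Section 9.5.2.9 does not say which of up to 20 IIEF comparisons answers the 1-year erectile-function objective

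*Combined protocol and SAP*

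**What the plan says.** Section 2.2 lists, as key secondary objective 11, "Erectile function compared to baseline as assessed by the IIEF post RALRP at 1 year follow up". That is one construct at one time.

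Section 9.5.2.9, the matching analysis section, is wider. It states "Five subscales are calculated as follows" and lists Erectile Function (items 1-5 and 15), Orgasmic Function, Sexual Desire, Intercourse Satisfaction and Overall Satisfaction. It continues "Each subscale will be summarized separately for both treatment groups", at baseline and at the "3 month, 6 month, 9 month, and 12 month timepoints, including change from baseline". The test follows in a separate sentence: "Treatment means for the change from baseline will be compared using a matched pairs t-test". That sentence names no subscale and no month.

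Section 9 states no significance level, no multiplicity rule and no ordering among outcomes. On size, Section 9.2 says "This is a proof of concept study and therefore, formal sample size calculations were not performed". Section 9.1 places all analyses on a database locked once every patient has completed Visit 7, died or been lost to follow-up. Section 5.7 lists Visits 6, 7, 8 and 9 as Months 3, 6, 9 and 12, so Visit 7 is Month 6 and the 1-year visit is Visit 9.

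**The concern.** Objective 11 is specific, but its analysis section is not. Four of the five subscales measure something other than erectile function, and three of the four months are not one year. On the wider reading, 19 of the 20 possible comparisons do not match the objective's wording, yet nothing in 9.5.2.9 ranks them below the one that does.

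Other analysis sections show that the plan can be this specific. Section 9.5.2.7 ties biochemical recurrence, also a 1-year objective, to Visit 9. Sections 9.5.2.1 and 9.5.2.2 tie hemoglobin and hematocrit to the first post-operative day.

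What is at stake is selective emphasis in either direction. Section 1.2 hypothesises better functional outcomes, and Section 1.3 argues that selective embolization should not cause impotence. A favourable or unfavourable subscale and month could be presented as the answer to objective 11 without departing from the plan as written.

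**Working it through.** The plan gives no alpha, power or error rate for this outcome, so there is no stated figure to reproduce.

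**Inputs**
- Subscales: 5 (9.5.2.9).
- Post-baseline months: 4 (9.5.2.9).
- Pairs: 10, since Section 4 has the PAE patients "matched with 10 controls who will not receive pre-prostatectomy PAE". A paired t-test then has 9 degrees of freedom.
- Significance level: not stated. Assumed two-sided 0.05 per test, in line with the 95% intervals that 9.5.1 asks for ("including 95% confidence intervals for the means").
- Correlation among the comparisons: not stated. Assumed from 0 to 0.9, between subscales and between months.

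**Step 1. Count.** 5 × 4 = 20 comparisons on the wider reading.

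**Step 2. Expected false positives with no true effect.** 20 × 0.05 = 1.0, whatever the correlation.

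**Step 3. Chance of at least one, if independent.** 1 − 0.95^20 = 64.2%.

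**Step 4. Chance of at least one, if correlated.** Null simulation with 40,000 replicates, 10 pairs, a two-sided paired t-test at 0.05, and equal correlations between subscales and between months (the correlation between different subscales at different months is the product of the two):

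| Correlation, subscales / months | Any of 20 | Five subscales, Month 12 only | Erectile Function, four months | Erectile Function, Month 12 |
|---|---|---|---|---|
| 0 / 0 | 64.1% | 22.4% | 18.6% | 5.0% |
| 0.3 / 0.3 | 59.2% | 21.2% | 17.2% | 5.0% |
| 0.5 / 0.5 | 51.0% | 19.1% | 16.1% | 4.9% |
| 0.5 / 0.7 | 44.9% | 19.1% | 13.7% | 4.8% |
| 0.7 / 0.7 | 38.5% | 16.0% | 13.9% | 5.0% |
| 0.8 / 0.8 | 29.5% | 13.6% | 12.1% | 5.0% |
| 0.9 / 0.9 | 20.1% | 11.1% | 10.1% | 5.2% |

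The first row agrees with the exact values: 64.2%, 1 − 0.95^5 = 22.6% and 1 − 0.95^4 = 18.5%. Loss of pairs changes little: with 8 pairs and correlations of 0.6 / 0.7 the figure for any of 20 is 42.6%.

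**Step 5. Ratio to one designated test.** 20.1 / 5 ≈ 4 and 64.2 / 5 ≈ 13.

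**Step 6. The alternative of adjusting all 20.** Bonferroni gives 0.05 / 20 = 0.0025 per test. For an assumed standardized paired difference of 1.0, the noncentrality is 1.0 × √10 = 3.16 on 9 degrees of freedom. Power is 80.3% at 0.05 and 26.8% at 0.0025. Designating one comparison costs much less than adjusting all 20.

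**Step 7. The lock.** If only Months 3 and 6 were complete at a lock after Visit 7, there would be 5 × 2 = 10 comparisons and 1 − 0.95^10 = 40.1% if independent. The Month 12 comparison that the objective needs could then be incomplete.

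**The case against.** **Does the text prescribe 20 tests?** A reader might infer that it does. It does not say so. It prescribes summaries for each subscale at each month, and the test sentence stands apart. Twenty is the natural reading and the upper count. This objection stands, and the defect is ambiguity.

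**Is a chance finding likely?** A reader might infer so from the 64%. That figure needs independence, which is implausible for subscales of one questionnaire repeated in the same pairs. Change scores within a subscale share a baseline value. In Appendix E, items 1 to 10 each have a zero answer for no activity, stimulation, intercourse or attempts, so an inactive patient scores low on three subscales at once. In the table the risk exceeds one half only with correlations of about 0.5 or lower, and the documents give no correlations. This objection stands too.

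**Is the comparison already identifiable?** Objective 11, the section title and the name of the first subscale all point to Erectile Function at one year. That makes the remedy uncontroversial, but 9.5.2.9 neither names that comparison as the main one nor sets the other comparisons below it.

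**Does any decision depend on it?** A reader might infer that the objective could be formally declared met or missed. The plan has no success criterion, and Section 9.2 describes a proof-of-concept study. So the risk is selective reporting of a secondary outcome. Exploratory status lowers the priority but does not tell the analyst which test answers an objective that the protocol calls key.

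**Is the IIEF being singled out?** Continence in 9.5.2.8 also has five timepoints and none is singled out. That is a fair observation, but objective 9 fixes no time, so it lacks the mismatch seen here.

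**Conclusion.** The point holds as a low-priority clarification. Objective 11 asks about one construct at one year; 9.5.2.9 can be read as up to 20 unadjusted comparisons and does not say which of them is the answer. With no true effect, the chance of at least one false positive is about 20% to 64%, roughly 4 to 13 times the 5% of a single designated test. The range rests on an assumed two-sided 0.05 per test, all 20 comparisons being tested, and assumed correlations from 0.9 down to 0. The documents do not support the stronger statements that a false positive is more likely than not, that 20 tests are expressly prespecified, or that a pass/fail decision depends on them. Separately, the lock after Visit 7 in Section 9.1 conflicts with a Month 12 comparison being complete when analysed.

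**What to change.** 1. In 9.5.2.9, state that objective 11 is answered by one comparison: change from baseline to Month 12 (Visit 9) in the Erectile Function subscale (items 1-5 and 15), by the matched pairs t-test already planned, with its significance level stated.
2. In the same section, label all other subscale and month comparisons as descriptive and report them as estimates with 95% confidence intervals, which 9.5.2.9 does not currently request. The label matters more than whether p-values are printed, because an interval that excludes zero carries the same message.
3. Reconcile the Visit 7 lock in Section 9.1 with the Visit 9 assessment, so that the designated comparison is complete at lock.

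Items 1 and 2 are a sentence or two and need no added patients, visits or data collection. The downside is that the other subscales and months become descriptive only. If item 3 is resolved by a later lock, final analyses would wait for the Month 12 visits, which Section 4 already includes in its minimum of 12 months of follow-up.

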### **9.5.3 Additional Secondary Efficacy Outcomes – PAE Patients Only**

#### **9.5.3.1 Change in Prostate Volume**

An analysis of the change in prostate volume between baseline (pre-PAE) and Visit 3 as determined by MRI will be performed. Each PAE patient will have their prostate volume measured at both timepoints and the change will be calculated. Summary data will be presented for both timepoints and the change from baseline, including 95% confidence intervals.

